#### 16.3.2.3 Adverse Events

Determine acute and late effect toxicity after radiotherapy treatment targeting dose escalated volumes defined to include high F-DOPA-PET uptake. The rate of acute and late treatment-related toxicities for newly diagnosed high-grade glioma patients treated with F-DOPA PET image-guided hypofractionated proton beam therapy will be determined, with acute RT toxicities graded using Common Terminology Criteria for Adverse Events (CTCAE) v4.0 (available at <http://ctep.cancer.gov>).

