### **2.2 Secondary**

2.2.1 Compare progression free survival at 12 months after radiation therapy targeting volumes designed with both F-DOPA-PET and conventional MR image information with historical controls.

2.2.2 Determine acute and late effect toxicity after hypofractionated proton beam radiotherapy treatment including areas of high F-DOPA-PET uptake (T/N>2.0)

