#### 4.0 Test Schedule

Tests and procedures	Pre-Treatment	Treatment Phase and Active Monitoring			Observation/Follow-up
	<math>\leq 21</math> days prior to registration	Prior to RT	Cycle 1 RT and Chemo	Cycle 2-7 Chemo	
Physical exam, wt, ECOG PS	X			X	X
Neuro history and exam	X			X	X
CBC with differential	X			X	X
 F-DOPA adverse event assessment 		X			
 F-DOPA PET/MRI 		X			
Assessment of Concurrent steroids and anticonvulsants		X 		X	X
CT simulation 3		X			
Toxicity assessment 	X		X	X	X
EORTC QLQ-C30 		X		X	X
EORTC QLQ-BN20 		X		X	X
MMSE 	X			X	X
Advanced MRI 		X		X	X
Proton Beam RT			X		
Temozolomide			X	X	

1. The timing of follow-up visits for each patient will be per the clinician's discretion from the end of Cycle 7 until death or 2 years post-RT.

2. F-DOPA post-injection assessment: done approximately 15-20 minutes post injection of F-DOPA and if AE observed a second AE assessment is required  $\leq 24$  hours post injection.

3. CT simulation can be done prior to or after registration, but before RT start.

4. Baseline and cycle 1 toxicities to be assessed by Radiation Oncologist, cycles 2-7 to be assessed by Neuro-oncologist. Toxicity assessment completion window during RT and chemotherapy is +/- 1 week.

5. May be done any time before registration, but must be completed prior to start of RT. Patients will complete a maximum of 6 post-baseline QOL/MMSE evaluations

6. Must be completed prior to first F-DOPA injection.

7. Post-RT scans during Cycles 2-7 must be completed every 2 months (+/- 2 weeks). All other tests and procedures in Cycles 2-7 will be completed when the patient is seen at the clinician's discretion.

8. F-DOPA PET/CT + diagnostic MRI is an acceptable alternative to F-DOPA PET/MRI

9. Advanced MRI is performed per standard clinical care in Arizona. Rochester will perform either MRI or advanced MRI at the physician's discretion.

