### **10.3 Attribution to agent(s) or procedure**

Patients will be observed for adverse events for approximately 15-20 minutes post  $^{18}\text{F}$ -DOPA injection by the Nuclear Medicine health professionals administering the scan.

Patients will be regularly evaluated by a radiation oncology health professional per standard clinical practice throughout their course of external beam radiation therapy.

When assessing whether an adverse event is related to a medical treatment or procedure, the following attribution categories are utilized:

Definite - The adverse event *is clearly related* to PET scanning and  $^{18}\text{F}$ -DOPA injection

Probable - The adverse event *is likely related* to PET scanning and  $^{18}\text{F}$ -DOPA injection

Possible - The adverse event *may be related* to PET scanning and  $^{18}\text{F}$ -DOPA injection

Unlikely - The adverse event *is doubtfully related* to PET scanning and  $^{18}\text{F}$ -DOPA A injection

Unrelated - The adverse event *is clearly NOT related* to PET scanning and  $^{18}\text{F}$ -DOPA injection

Definite - The adverse event *is clearly related* to hypofractionated proton beam therapy.

Probable - The adverse event *is likely related* to hypofractionated proton beam therapy.

Possible - The adverse event *may be related* to hypofractionated proton beam therapy.

Unlikely - The adverse event *is doubtfully related* to hypofractionated proton beam therapy.

Unrelated - The adverse event *is clearly NOT related* to hypofractionated proton beam therapy.

**Events determined to be possibly, probably or definitely attributed to a medical treatment suggest there is evidence to indicate a causal relationship between the drug/treatment and the adverse event.**

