#### 10.4.2 Special situations to Expedited Reporting

##### Exceptions to Expedited Reporting: EXPECTED Serious Adverse Events

An expedited report may not be required for specific Grade 1, 2 and 3 Serious Adverse Events where the AE is EXPECTED. Any protocol specific reporting procedures MUST BE SPECIFIED BELOW and will supersede the standard Expedited Adverse Event Reporting Requirements: Hospitalizations for reasons deemed to be disease related will not be reported.

PET scanning and PET tracer injection are the only procedures unique to this study. The use of hypofractionated radiation therapy is an acceptable form of treatment per National Comprehensive Cancer Network (NCCN) guidelines. All other aspects of radiation therapy and follow-up are part of standard brain cancer treatment. Consequently, only adverse events possibly, probably, or definitely related to F-DOPA-PET administration or radiotherapy will be graded and reported in this protocol. All other toxicities associated with other components of conventional brain cancer treatment (e.g. hematological events resulting from chemotherapy) will not be graded or reported as part of this protocol

System Organ Class (SOC)	Adverse event/ Symptoms	CTCAE Grade at which the event will not be expeditedly reported.
General disorders and administration site conditions	Fatigue	≤Grade 3
Immune system disorders	Allergic Reaction	≤Grade 3
Nervous system disorders	Central nervous system necrosis	≤Grade 3
Nervous system disorders	Vasovagal reaction	≤Grade 3
Injury, poisoning and procedural complications	Bruising	≤Grade 3
Skin and subcutaneous tissue disorders	Rash maculo-papular	≤Grade 3

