## 10.6 Required Routine Reporting

### 10.6.1 Baseline and Adverse Events Evaluations

CTCAE System/Organ/Class (SOC)	Adverse event/Symptoms	Baseline	Post Injection assessment 	Active Monitoring
General disorders and administration site conditions	Fatigue	x		x
Immune system disorders	Allergic reaction		x	
Nervous system disorders	Central nervous system necrosis			x
Nervous system disorders	Vasovagal Reaction		x	
Injury, poisoning and procedural complications	Bruising	x	x	
Skin and subcutaneous tissue disorders	Rash maculo-papular	x	x	
Skin and subcutaneous tissue disorders	Alopecia	x		x
Investigations	Lymphocyte count decreased	x		x
Investigations	Platelet count decreased	x		x
Investigations	Weight loss	x		x
Metabolism	Anorexia	x		x

CTCAE System/Organ/Class (SOC)	Adverse event/Symptoms	Baseline	Post Injection assessment 	Active Monitoring
Nervous system disorders	Encephalopathy	x		x
Nervous system disorders	Headache	x		x
Nervous system disorders	Seizure	x		x
Psychiatric disorders	Confusion	x		x

1. This assessment should occur approximately 15-20 minutes post injection (after scan is completed)

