#### 10.6.2 Additional instructions

Submit via appropriate MCCC Case Report Forms (i.e., paper or electronic, as applicable) the following AEs experienced by a patient and not specified in Section 10.6.

10.6.2.1 Grade 2 AEs deemed *possibly, probably, or definitely* related to the study treatment or procedure.

10.6.2.2 Grade 3 and 4 AEs regardless of attribution to the study treatment or procedure.

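### The toxicity summary counts only treatment-related events and leaves the solicited baseline grades unused, so rates of neurological symptoms can move on attribution alone

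*Combined protocol and SAP*

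**What the plan says.** All references are to the combined protocol and SAP.

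- **Objective.** Section 2.2.2 is not limited to related events: "Determine acute and late effect toxicity after hypofractionated proton beam radiotherapy treatment including areas of high" tracer uptake.
- **Collection.** The table in Section 10.6.1, "Baseline and Adverse Events Evaluations", marks ten terms under both Baseline and Active Monitoring: fatigue, alopecia, lymphocyte count, platelet count, weight loss, anorexia, encephalopathy, headache, seizure and confusion. CNS necrosis is marked under Active Monitoring only.
- **Analysis.** Section 16.3.2.3 plans one quantity: "The rate of acute and late treatment-related toxicities" in patients given the PET-guided proton regimen. It mentions neither the baseline grade, nor worsening, nor a summary regardless of attribution.
- **Attribution.** Section 10.3 gives five levels, once for PET and tracer and once for proton therapy. It adds: "Events determined to be possibly, probably or definitely attributed to a medical treatment suggest there is evidence to indicate a causal relationship". It has no scale for temozolomide or for tumour, and no rule for a symptom already present at baseline.
- **Assessors.** Section 4.0, footnote 4: "Baseline and cycle 1 toxicities to be assessed by Radiation Oncologist, cycles 2-7 to be assessed by Neuro-oncologist".
- **Filter on recording.** Section 10.4.2: "Consequently, only adverse events possibly, probably, or definitely related to" the PET tracer or radiotherapy are to be graded and reported, with chemotherapy blood-count events given as an example of what is left out. Section 10.6.2, for events outside the solicited list, asks for "Grade 3 and 4 AEs regardless of attribution to the study treatment or procedure".

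**The concern.** Headache, seizure, confusion and encephalopathy can come from the tumour as well as from irradiation, and no concurrent control arm shows the background level. A rate restricted to events judged treatment-related therefore depends on a judgement made patient by patient, without blinding, and for which the plan gives no rule.

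The error can go either way. A radiation effect put down to the tumour drops out of the rate. A symptom that was there before treatment and has not changed can enter it if someone marks it as possibly related. The baseline grades that would show the difference are solicited, but no analysis uses them. At stake is the interpretation of secondary objective 2.2.2 for the neurological terms, in a trial whose toxicity results will be read against other hypofractionated regimens.

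**Working it through.** **1. Is there a figure to reproduce?** No. The plan states no toxicity rate, margin or power for Section 16.3.2.3. The check is a comparison of sections, followed by an illustration with assumed counts.

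**2. What the plan offers to support attribution.** There is no control arm (Section 16.1). The assessor changes after cycle 1 (Section 4.0). The attribution scales omit temozolomide and tumour (Section 10.3). The protocol itself treats tumour and treatment effect as hard to tell apart: it defines pseudoprogression (Section 11.4.1.5) and waits more than 3 months after radiotherapy before accepting progression (Section 13.4). None of this measures reliability, but none of it allows reliability to be assumed.

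**3. How far attribution alone can move the rate.** Inputs:
- n = 39 evaluable patients (Section 16.2).
- A = 16 patients with a given symptom at any time after baseline (assumed).
- W = 8 of those 16 with a grade worse than at baseline (assumed).
- s = share of the 16 called related, varied from 10% to 90% (assumed).

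Planned rate = s × A / n, rounded to whole patients. Worsening rate = W / n. Intervals are exact (Clopper-Pearson) 95%.

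| Quantity | Count | Rate | 95% CI |
|---|---|---|---|
| Any post-baseline symptom | 16/39 | 41% | 26–58% |
| Related, s = 10% | 2/39 | 5% | 1–17% |
| Related, s = 25% | 4/39 | 10% | 3–24% |
| Related, s = 50% | 8/39 | 21% | 9–36% |
| Related, s = 75% | 12/39 | 31% | 17–48% |
| Related, s = 90% | 14/39 | 36% | 21–53% |
| Worse than baseline, any cause | 8/39 | 21% | 9–36% |

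The symptoms are identical in every row marked related. At s = 10%, at least 8 − 2 = 6 patients who worsened are left out. At s = 90%, at least 14 − 8 = 6 patients who are counted had no worse a symptom than before treatment. At s = 50% the two rates agree in number, but they need not describe the same 8 patients.

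**4. Range over the assumed counts.** Before rounding, the spread between s = 10% and s = 90% is 0.8 × A / 39:
- A = 8: 6.4/39 = 16 percentage points.
- A = 16: 12.8/39 = 33 points.
- A = 24: 19.2/39 = 49 points.

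The worsening rate depends on W only: 4/39 = 10%, 8/39 = 21%, 12/39 = 31%. It does not move with s.

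**5. Are the on-study grades assured?** Not as written. Section 10.6.1 solicits them with no attribution condition. Section 10.4.2 says only related events are graded and reported, and excludes chemotherapy blood-count events, although 10.6.1 solicits lymphocytes and platelets. Section 10.6.2 collects severe events whatever the attribution, which also conflicts with 10.4.2, but it covers only events outside the solicited list and so does not secure the ten terms.

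**6. Would a split by progression work?** Not on confirmed progression. Footnote 2 to the response table in Section 11.4.1.5 requires more than 3 months since radiotherapy, central radiologic progression and clinical progression judged by the treating oncologist. Early tumour-driven worsening would therefore fall before confirmed progression by definition.

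**The case against.** The strongest case against has five parts.

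- **The plan is silent, not wrong.** The radiation oncologist grades both baseline and cycle 1, and nothing stops an assessor from weighing the baseline grade. This stands. A reader might infer that attribution here cannot be made reliably, or that baseline is disregarded when it is made. The documents support neither: they give no reliability figure and are silent on how baseline enters the judgement.
- **All-cause worsening is not toxicity either.** It counts tumour progression, in a population for which Section 16.2 assumes a median survival of 7.5 months. This stands, and it decides how the table must be labelled. It does not restore the related-only rate as a sufficient summary.
- **The data may not be there.** Section 10.4.2 could filter out unrelated on-study grades. This stands, and it means that attribution may limit recording as well as analysis.
- **Patient-reported outcomes already cover it.** Section 16.4.3 plans change from baseline for the EORTC scales, which include headache, seizures, hair loss, fatigue and appetite, and MMSE is repeated. This stands in part. These are not CTCAE grades, and there is no encephalopathy item.
- **It is a descriptive secondary endpoint.** Section 16.3.2.3 has no test or decision rule. This stands: the primary endpoint is untouched.

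**Conclusion.** The point holds as a gap in the analysis plan. Ten terms are solicited at baseline and on study, the single planned summary uses attribution and not the baseline grade, and in this single-arm setting attribution of neurological symptoms cannot be assumed reliable. Under the assumed counts (16 of 39 with the symptom, 8 worse than baseline), the planned rate runs from 5% to 36% while worsening stays at 21%. The counts are illustrative; the size scales with how common the symptom is.

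Two further inferences should be resisted. A reader might take the 21% as the true toxicity rate; it is an all-cause figure and carries no causal claim. A reader might also suppose that the remedy captures the harm that motivates the trial, symptomatic radiation necrosis. It does not, because that term has no baseline grade in Section 10.6.1. Nor does it reach late effects, which Section 10.6.3 puts on the RTOG/EORTC scale.

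**What to change.** 1. In Section 16.3.2.3, for the ten terms with both grades, add two proportions regardless of attribution: maximum post-baseline CTCAE grade at least one grade worse than baseline, and worsening from baseline to grade 3 or higher. State the denominator as patients with a baseline grade and at least one on-study grade, and show the number missing. Keep the treatment-related table beside it.
2. Label the new table as all-cause worsening, not as a causal toxicity rate.
3. Reconcile Section 10.4.2 with Sections 10.6.1 and 10.6.2, so that on-study grades of the solicited terms are recorded whatever the attribution.
4. If the table is split by progression, use the date of first documented progression, including preliminary progression, instead of confirmed progression.

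The cost is one extra table and complete recording of grades that Section 10.6.1 already solicits. The drawback is that the new rate includes tumour-driven worsening, which the label must make plain. No additional assessment is needed beyond those in Section 10.6.1.

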### 16.4 Correlative Research

16.4.1 Compare RT treatment volumes defined by MR only with RT treatment volumes defined with both PET and MR information. To assess the impact of integrating PET on target definition, the treating radiation oncologists will first define the treatment volumes for CTVMR and using the MR images while blinded to the PET study. Then the PET study will be reviewed with the planning CT and MRI studies to allow contouring of the CTVPET defined by the T/N ratio of >2.0, respectively. The contours will be combined by the treating radiation oncologist and then expanded as described above. The volume of overlap and non-overlap between the CTV defined by MR and that defined by PET will be calculated. Similarly, the MR-only defined volumes will be compared against the volumes defined with the combination of MR and PET planning. Paired t-test statistical analysis will be performed to determine if any differences exist and the level of statistical significance between treatment volumes defined by MR only and treatment volumes

defined with both PET and MR information. Alternate metrics for comparison will also be assessed, including spatial overlap, distance, correlations and 3D shape comparisons.

16.4.2 Compare differences in RT volumes identified using biopsy-validated thresholds as highly aggressive disease comparing F-DOPA uptake and relCBV from pMRI as well as differences in RT volumes identified using biopsy-validated thresholds as tumor extent comparing F-DOPA uptake and diffusion maps from DTI will be evaluated. Paired t-test statistical analysis will be performed to determine if any differences exist and the level of statistical significance between RT volumes based on F-DOPA uptake and the measures mentioned above.

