### 1.5 F-DOPA correlation with pathologic tissue

F-DOPA-PET has been in production at Mayo Clinic Rochester since 2001, used to image Parkinson's patients to study the F-DOPA uptake in the caudate nucleus and putamen. Due to the imaging potential of F-DOPA-PET for gliomas, an initial study by [name] et al. correlated F-DOPA-PET against conventional MRI for neurosurgical biopsy targeting, resection planning and radiotherapy target volume delineation. Pathologic review confirmed glioma in 22 of 23 biopsy specimens. Thirteen of 16 high-grade biopsy specimens were obtained from regions of elevated F-DOPA uptake, while T1-CE was present in only 6 of those 16 samples. Optimal F-DOPA-PET thresholds corresponding to high-grade disease based on histopathology were calculated as Tumor uptake/Normal tissue uptake (T/N) > 2.0. In every patient, F-DOPA uptake regions with T/N > 2.0 extended beyond T1-CE up to a maximum of 3.5 cm. SUV was found to correlate with grade and cellularity.

[figure not shown]

Fig. 5. Registered F-DOPA PET-CT (A), T1-CE MRI (B), and T2-FLAIR MRI (C) contours drawn by the neuroradiologist and the F-DOPA representing the region of high-grade disease components defined by T/N > 2.0.

[name] et al. Neuro Oncol 2013 Aug; 15(8), 1058-1067

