#### 7.1.9 Contouring and Target Definition (please refer to diagram below)

1. Co-registration with CT scans, MRI scans, and PET scans will be used in identifying the CTV volumes
2. The doses prescribed will be based on the boolean(combined) volume of CTV defined by the PET( $T/N \geq 2.0$ ) and the MRI areas of contrast enhancement including the surgical cavity.
  - a. For patients with a combined volume  $\leq 65$  cc, over five treatment days, patients will receive 35 Gy to CTV3500\_PET, 30 Gy to CTV3000\_MR and 25 Gy(CTV2500) to boolean(combined) volume of CTV3500\_PET+CTV3000\_MR+1cm.
  - b. For patients with a combined volume  $> 65$  cc, over ten treatment days, patients will receive 40 Gy to CTV4000\_PET, 35 Gy to CTV3500\_MR and 30 Gy(CTV3000) to boolean(combined) volume of CTV4000\_PET+CTV3500\_MR+1cm.
3. The optimization target volume (OTV) is defined as a margin of 2 mm isotropic expansion of the CTV and edited clinically based on patterns of tumor spreading and anatomic boundaries such as skulls and nasal cavity.
4. All normal structures will be contoured on the standard of each institution.

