#### Ten Fraction Regimen ( $> 65\text{cc}$ )

$\text{CTV4000\_PET} = \text{PET T/N} > 2.0$   
 $\text{CTV3500\_MR} = \text{Boolean}(\text{T1\_Gad} + \text{T1\_Cavity})$   
 $\text{Boolean CTV4000\_PET} - \text{CTV3500\_MR} > 65\text{cc}$   
 $\text{CTV3000} = (\text{Boolean CTV3500\_PET} + \text{CTV3000\_MR}) + 1\text{cm}$

Optimization Target Volume (OTV)  $\geq 2\text{mm} + \text{CTV3000}$

\*Need to make sure all CTVs are inside the brain tissue contour

\*Need to evaluate inclusion or exclusion of small CTV volumes at a considerable distance from bulk CTV volumes

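### In 16.4.1 the combined volume contains the MR-only volume, so a t-test for a difference says little about how much PET adds, and matched expansion and editing are not stated

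*Combined protocol and SAP*

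**What the plan says.** In 16.4.1 the treating radiation oncologist contours the MR volume first, blinded to PET, and then contours the PET volume from the T/N threshold. Next, "The contours will be combined by the treating radiation oncologist and then expanded as described above". Two kinds of comparison follow. One is descriptive: "The volume of overlap and non-overlap between the CTV defined by MR and that defined by PET will be calculated". In the other, "the MR-only defined volumes will be compared against the volumes defined with the combination of MR and PET planning". The named inference is: "Paired t-test statistical analysis will be performed to determine if any differences exist and the level of statistical significance between treatment volumes". A closing sentence adds further metrics (spatial overlap, distance, correlation, 3D shape). The section gives no significance level, number of pairs, target difference or confidence interval.

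Section 7.1.9 defines the combination: "The doses prescribed will be based on the boolean(combined) volume of CTV defined by the PET" and by MRI enhancement plus cavity. The 1 cm margin is attached to that combination, as in "25 Gy(CTV2500) to boolean(combined) volume of" the two CTVs. The size-rule lines in the two regimen boxes print a minus sign. The numbered text and the expanded-volume lines use plus, so the combination is read here as a union. The ten-fraction box also tells the planner to "evaluate inclusion or exclusion of small CTV volumes at a considerable distance from bulk CTV volumes" and to keep CTVs inside the brain contour.

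**The concern.** A union cannot be smaller than one of its parts. If the two volumes are handled alike, the null hypothesis of no difference is false as soon as one patient has uptake outside the MR contour. The nearest evidence in the protocol suggests that this is common. Section 1.5 reports that, in every patient of the pilot study, "uptake regions with T/N > 2.0 extended beyond T1-CE up to a maximum of 3.5 cm". That comparator was enhancement without the surgical cavity, so the extent may be less here.

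Goal 2.3.1 asks how the two volumes compare, and the test result would mostly confirm that they differ. The comparator is also not fully defined. Expansion is described only for the combined contours, and nothing says that editing is the same on both sides. If it is not, the difference mixes the effect of PET with the effect of a margin or an edit. At stake is what this correlative aim can conclude.

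**Working it through.** **Inputs.** 39 evaluable patients, at most 43 (16.2.2). Union and 1 cm margin (7.1.9). Two-sided 0.05 is assumed. The documents give no distribution for MR volumes or PET additions, so those below are assumptions. Section 16.4.1 states no power or effect size, so there is no figure to reproduce.

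**1. Sign.** V(MR ∪ PET) − V(MR) = V(PET outside MR) ≥ 0. With 1 cm added to both, the expanded union still contains the expanded MR volume, so the difference is again ≥ 0, but its amount changes. For a 40 cc sphere to which PET adds 30%, the difference is 12 cc with both unexpanded and 25.2 cc with both expanded. The basis therefore has to be named.

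**2. Size and p-value.** t = mean(d) / (SD(d)/√n). Multiplying every difference by the same constant leaves t unchanged, so p depends on how variable the additions are relative to their mean, not on how many cc they are. In the simulation (n=39, 20,000 trials per cell) MR volume is log-normal and every patient is affected. The share of trials with p<0.001 was:

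| PET adds (uniform, % of MR volume) | log-SD 0.3 | log-SD 0.6 | log-SD 0.9 |
|---|---|---|---|
| 0–2% (mean 1%) | 1.000 | 0.998 | 0.933 |
| 30–60% (mean 45%) | 1.000 | 1.000 | 0.977 |

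A 45-fold change in the added volume hardly moves the result.

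**3. Unmatched margin (illustration).** R = (3V/4π)^(1/3) and V′ = (4/3)π(R+1)³, in cm and cc. If only the combined volume is expanded and PET adds nothing:
- 25 cc: R = 1.81, V′ = 93 cc, gain 68 cc
- 65 cc: R = 2.49, V′ = 179 cc, gain 114 cc
- 130 cc: R = 3.14, V′ = 298 cc, gain 168 cc

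Real gains would be smaller, because CTVs are kept inside the brain.

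**4. Unmatched editing (illustration).** Assume that 36% of patients gain 0–2% of MR volume. Rejection is then 91–100%. Now let an independent 20% of patients lose 0–5% because the combined volume alone is edited. The expected net change is 0.36 × 1% − 0.20 × 2.5% = 0.36% − 0.50% = −0.14% of MR volume. Rejection falls to 4–6%, and the mean difference is negative in 66–73% of simulated trials.

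**5. Few patients affected (illustration).** If k of n non-negative differences are non-zero, t ≤ √(k(n−1)/(n−k)), reached when they are equal. For n=39:
- k=1: t=1.00, p=0.324
- k=2: t=1.43, p=0.160
- k=3: t=1.78, p=0.083
- k=4: t=2.08, p=0.044

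With one to three patients affected the test cannot reach 0.05, however large the volumes. A confidence interval for the mean is also weak in this setting. With 5% of patients affected, a 95% percentile bootstrap interval covered the true mean in 69–86% of trials, against 91–94% with all affected. The proportion stays interpretable: 3 of 39 is 7.7%, exact 95% CI 1.6–20.9%.

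**The case against.** The strongest reply is that 16.4.1 already measures size. It plans overlap and non-overlap volumes and several alternate metrics, and a paired t-test carries a mean difference and standard error from which an interval follows directly. This stands in part. A reader might infer that the plan has no measure of how much PET adds, and the text does not support that. What is missing is an interval, or any instruction to report the mean. The only inference named is a test of existence, and reporting the mean would not settle the expansion question.

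A reader might also infer that the sign is always fixed and significance guaranteed. That fails under one-sided editing, which the planning notes leave open. In the editing case above, with the loss held fixed, rejection did track size: 4–6% for additions of 0–2%, 44–69% for 0–10% and 95–100% for 30–60%. The argument therefore holds only when handling is matched.

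The 36% in section 1.6 might be read as 14 of 39 patients affected and the rest with nothing. The text says that 36% had more than 30% of high-density disease outside enhancement. It does not say that the other 64% had none, and its denominator is not the MR volume. It supports neither a rejection rate nor a reporting threshold here. Nor do the documents suggest that only one to three patients will have PET-only volume.

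Lastly, 7.1.9 defines unexpanded MR and PET CTVs, so a like-for-like comparison is available. It would be wrong to conclude that the comparison will be made unmatched. The plan does not say which it will be.

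**Conclusion.** The point holds in a limited form and is minor. With identical expansion and editing, the paired difference is the volume PET adds (measured on expanded volumes if both are expanded) and is never negative, so the planned p-value says little about its amount. Without identical handling, the difference no longer measures PET. The size of the first problem rests on assumed distributions, 39 pairs and every patient having some PET-only volume. The sphere, editing and few-affected figures show direction and possible scale; they are not estimates for this trial. The point concerns goal 2.3.1 only and does not affect the primary endpoint, safety, treatment or 16.4.2.

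**What to change.** Change the wording of 16.4.1 only.

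1. State that, for this analysis, the MR-only and combined volumes are compared with identical expansion (both unexpanded, or both plus 1 cm; say which) and identical editing, including that of small remote volumes.
2. Replace the t-test p-value as the stated inference with the PET-only volume, that is, the part of the planned non-overlap that lies outside MR. Report it in cc and as a percentage of the MR volume, with median, quartiles, range, and mean with 95% CI. A percentile bootstrap interval cannot go below zero. A t interval can: with 3 of 39 equal volumes v it runs from −0.011v to 0.164v.
3. Add the proportion of patients with any PET-only volume, with an exact CI, counting patients with no T/N>2.0 region as zero.
4. If few patients are affected, rely on that proportion and a listing of individual volumes.

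The overlap and non-overlap volumes are already to be calculated, so no new scans, data or patients are needed. The one small loss is that the aim no longer carries a headline p-value.
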